Primary Hypothesis	Very low-dose intravenous tissue-type plasminogen activator (24 mg) + standard anticoagulation therapy (intravenous heparin) for treatment of acute PE in intermediate risk patients will have clot lysis of at least 15% by chest CTA at 24 \pm 6 hours post infusion compared with baseline CTA. All patients will be treated with oral apixaban at the approved dose of 10 mg twice-daily starting at least 24 hours after completion of the IV study drug for seven days followed by 5 mg twice-daily for at least 6 months, with the potentiality of decreasing the apixaban dose again to 2.5 mg twice-daily after 6 months.
	This is a randomized, double-blinded, placebo-controlled, single-center study intended to investigate very low dose systemic (IV) tPA along with standard anticoagulation therapy as a treatment for intermediate-high risk (submassive) PE. The study is planned to evaluate the reduction in clot burden based on the obstruction index using the Refined Modified Miller Score (RMMS), improvement in right ventricular (RV) function, and overall safety in the two treatment groups. Subjects with intermediate-high risk PE (hemodynamically stable PE with significant clot burden a RV dysfunction an at least one elevated biomarkers,will be randomized to one of two treatment groups: 24mg of systemic (IV) tPA + IV unfractionated heparin versus saline placebo + IV unfractionated heparin.
	Approximately 40 subjects will be enrolled. These subjects will be randomized in a 1:1 ratio (approximately 20 per treatment arm) to receive 24 mg tPA [Activase (alteplase)] + standard anticoagulation therapy (intravenous heparin) vs placebo + standard anticoagulation (intravenous heparin) therapy.
Study Design and Methodology	Upon enrollment, the standard of care labwork, chest contrast-enhanced computed tomographic angiogram (chest CTA), echocardiogram and duplex ultrasound of lower extremities will be reviewed The sPESI core will be calculated.

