3.4. CONCOMITANT TREATMENTS

3.4.1 PROHIBITED AND/OR RESTRICTED TREATMENTS

The following systemic medications may increase the risk of bleeding and will not be concurrently administered during the study:

- Other antithrombotic agents such as vitamin K antagonists (i.e., warfarin)
- Other factor Xa inhibitor oral anticoagulants (e.g. rivaroxaban, edoxaban, or betrixaban)
- Fondaparinux or low molecular weight heparins
- direct thrombin inhibitors (dabigatran, argatroban, bivalirudin, lepirudin, etc.)
- glycoprotein IIb/IIIa antagonists during the thrombolytic infusion
- NSAIDS

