3.5. DISCONTINUATION OF SUBJECTS FROM TREATMENT

Discontinuation of alteplase

If a subject develops the following adverse events the alteplase infusion will be permanently discontinued:

- SAE or other safety concern that is related to study drug treatment
- New onset of neurological symptoms
- New onset of severe headache
- Major life-threatening bleeding (per GUSTO criteria)
- Initiating or continuing study drug places the subject at undue hazard as determined by the Investigator

The subject will continue to be followed for the remainder of the study. The subject will be assessed immediately after the infusion and appropriate clinical treatment will be instituted.

One of the PIs will use his clinical judgment to determine the treatment needed and this may include imaging studies, blood transfusions and IVC filter placement. Once the subject is stabilized, if anticoagulant therapy is considered a clinical option, the subject will be started on apixaban per protocol.

Discontinuation of Apixaban

If a subject must be discontinued from apixaban before the end of the study, this will not result in automatic withdrawal of the subject from the study, and the subject should continue to be followed for efficacy and safety outcomes.

A subject should be discontinued from apixaban if:

- The investigator believes that for safety reasons (ie, adverse event) it is in the best interest of the subject to stop apixaban.
- The subject develops any condition which requires anticoagulation or thromboprophylaxis (ie, atrial fibrillation, VTE).
- The subject becomes pregnant.
- The subject requests to discontinue apixaban permanently
- The subject has a major life-threatening bleed (per GUSTO criteria);

If the subject permanently discontinues apixaban before the 6-month visit, he/she should be instructed to complete an unscheduled visit and the remaining scheduled visits. The investigator will provide a narrative to describe any adverse events that occur up to apixaban discontinuation. The appropriate adverse event or serious adverse event sections of the eCRF are to be completed.

A subject should have apixaban administration interrupted if the following conditions occur:

- Bleeding that is significant that does not fit GUSTO criteria
- Alanine transaminase (ALT) or aspartate transaminase (AST) ≥ 2 times upper limit of normal (ULN)
- Total bilirubin (TBL) ≥ 1.5 times ULN (except due to confirmed Gilbert's syndrome)
- Subjects with a significant drop in hemoglobin

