- Consider discontinuation / follow if Hgb < 10

The PI will use clinical judgment to determine course of action (labs, imaging studies, etc.) and decide when and if the apixaban can be restarted.

Withdrawal from the Study

A subject will be withdrawn from the study for any of the following reasons:

- Lost to follow-up (only after all means of all subsequent contact, including locator services where permitted by law) or,
- Withdrawal of consent (unless specifically refused by the subject. Subject contact will be made to obtain vital status and other outcomes at the 3, 6- and 12-month visit).

If a subject is lost to follow-up, every reasonable effort must be made by the study site personnel to contact the subject and determine the reason for discontinuation/withdrawal. The measures taken to follow up must be documented.

If a subject withdraws consent from study or is lost to follow-up, his or her vital status and other outcomes will be collected at the Day 30, 180 and 365 visits either by telephone or in person, or if applicable, by a review of the subject's medical or public records unless this contact is not allowed by local regulations.

Stopping rules at the interim analysis for the treatment (tPA) group would involve:

- Severe bleeding in the first 72 hours:
 - -One fatal intracranial hemorrhage (ICH)
 - -Two ICH of any kind
 - -Severe or life-threatening bleed rate of 15%; i.e., three patients (GUSTO criteria)

- Two cases of death from acute PE (in either group), if occurring during hospitalization (deterioration in a patient who survives will not be considered in stopping rules).
- Any other issue that the DMC believes merits discontinuing the trial.

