4. TREATMENTS

4.1. STUDY TREATMENTS

4.1.1. Investigational Product and Apixaban Administration

Tissue Plasminogen Activator (tPA) is a commercially available drug approved for fibrinolysis of PE by systemic infusion at the dose of 100mg. tPA [Activase (alteplase)] (24mg) or placebo will be prepared by the research pharmacy.

Apixaban is an oral anti-Xa anticoagulant approved by the FDA for the treatment and prevention of venous thromboembolic disease. Study subjects will take 10mg by mouth twice a day for 7 days and 5mg by mouth twice a day thereafter for 12 months.

4.1.2.. HANDLING AND DISPENSING

Systemic (IV) tPA

Systemic (IV) tPA used in the study will be procured from the research pharmacy and prepared following pharmacy procedures and manufacturer instructions.

IV unfractionated heparin (Standard of Care)

Unfractionated heparin will be administered intravenously and is approved by the FDA for the treatment and prevention of venous thromboembolic disease. Unfractionated heparin will be procured from the main hospital pharmacy and prepared following pharmacy procedures and manufacturer instructions.

Apixaban anticoagulant

Apixaban will be provided by BMS for the duration of the study. It will be stored and dispensed by the research pharmacy. Atter completion of the study, the treating physician will determine if apixaban should be continued based on current guidelines and expert opinion. If the treating physician desires continuation of treatment, the subject will obtain this medication via usual channels.

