Twenty-four hours after study drug administration, when the bleeding risk is determined to be low by the treating physician (i.e. no active bleeding nor significant hemoglobin drop $\geq 2 \text{ mg/dL}$), post-intervention evaluations are complete, the patient is tolerating oral medications, and the patient's creatinine clearance is >30 mL/min, the IV unfractionated heparin will be stopped. Provided bleeding risk is deemed acceptable, they will be immediately started on apixaban (Eliquis) 10 mg twice-daily x one week followed by 5 mg twice-daily for at least 6 months. Based on patient-specific factors, including unprovoked nature of PE event, and/or persisting DVT/PE risk factors, consideration will be given for decreasing the apixaban dose to 2.5 mg twice-daily after 6 months for the remainder of the study. The duration of total anticoagulation will be determined by the treating physician based on Clinic judgement, risk of recurrence, and whether the initial PE was provoked. Apixaban will be dispensed on Day 1, 30, and 180.

Timing of Thrombolytic Intervention

The subject will receive 24 mg of systemic (IV) tPA vs normal saline placebo within 24 hours of initiaition of anticoagulation therapy.

Systemic (IV) tPA

Commercially available formulation of systemic (IV) tPA (Genentech) may be used and all instructions for reconstitution provided in the package insert should be followed. tPA will be specially labeled for the study. The systemic (IV) tPA will be infused as follows: 4mg bolus followed by infusion at a rate of 20mg over 19 minutes for a total of 24mg.

Normal Saline Placebo

The pharmacy will prepare a normal saline placebo packaged in the same fashion as the systemic (IV) tPA. The saline will be infused as follows: 4mg bolus followed by infusion at a rate of 20mg over 19 minutes for a total of 24mg.

Day 0 Assessments: Pre-Infusion and Post-Infusion

- Vital signs including temperature, respiratory rate, heart rate, blood pressure, and oximetry will be obtained.
- Assessment of adverse events and bleeding events.

Day 1 Assessments

- Vital signs including temperature, respiratory rate, heart rate, blood pressure, and oximetry will be obtained.
- Physical Examination will be completed.

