- Within 24 ± 8 hours of discontinuing treatment, the subject will be assessed for improvement in PE signs and symptoms including sPESI score, repeat CT angiogram for determination of thrombus burden as measured by a Refined Modified Miller Score and RV/LV ratio, and an echocardiogram.
- Laboratory tests for Hgb, Hct, platelet count, aPTT, PT and INR, BNP, troponin, BUN and creatinine will also be obtained.
- Adverse events, VTE recurrence, and bleeding events will be recorded.

Day 2 Assessments

- Vital signs including temperature, respiratory rate, heart rate, blood pressure, and oximetry will be obtained.
- Laboratory tests for Hgb, Hct, platelet count, aPTT, PT and INR, BUN and creatinine will also be obtained.
- Adverse events, VTE recurrence, and bleeding events will be recorded.

Follow-up Clinic Visits and Subject Contact

- The subjects will be followed until Day 365 ± 15 days.
- A 72-hour follow-up assessment of Adverse Events will be conducted either in-person if the subject is still admitted at CSMC, or via telephone call if the subject is discharged.
- A Day 7 follow-up assessment of Adverse Events will be conducted via telephone call.
- The subject will return to the clinic Day 30, 180 and 365.
- The following assessments will be performed at follow-up clinic visits:
 - Echocardiogram at Day 30 and Day 180. Echocardiogram will be repeated at Day 365/EOT if last echocardiogram was abnormal.
 - Blood draw for laboratory tests, including hemoglobin, hematocrit, platelet count, BUN, creatinine, and liver function tests at Day 30.
 Physical exam and vital signs including respiratory rate, heart rate, blood pressure, temperature, and sPO2
 - o 6MWT with Borg score and requirement for oxygen therapy
 - Quality of life (QOL) as measured by the PROMIS PF-6 and Pulmonary Embolism Quality of Life (PEmb-QOL)
 - Adverse Events through 1 year follow-up.
 - Signs or symptoms of recurrent VTE
 - Changes in anticoagulant medications
 - Evidence of chronic thromboembolic disease or chronic thromboembolic pulmonary hypertension
- Phone calls for remote health checks will be conducted at Day 7, Day 90 ± 15 days and Day 270 ± 15 days.

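### Section 3.5 lists any new need for anticoagulation or thromboprophylaxis as a reason to stop apixaban, the trial's own anticoagulant, and names no replacement

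*Combined protocol and SAP*

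**What the plan says.** Section 3.5, under the heading on discontinuing apixaban, lists five reasons why a subject should come off the drug. One of them reads: "The subject develops any condition which requires anticoagulation or thromboprophylaxis (ie, atrial fibrillation, VTE". A second list follows, for temporary stops: "A subject should have apixaban administration interrupted if the following conditions occur". That list covers lesser bleeding, liver test elevations and falls in hemoglobin.

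Elsewhere apixaban is the planned oral anticoagulant for both arms. The synopsis states under Primary Hypothesis: "All patients will be treated with oral apixaban at the approved dose of 10 mg twice-daily", stepping down to 5 mg twice daily after seven days and continuing for at least 6 months. Section 4.1.1 says: "Apixaban is an oral anti-Xa anticoagulant approved by the FDA for the treatment and prevention of venous thromboembolic disease". Section 3.2 gives its bleeding profile as the reason for choosing it. The synopsis (Study Design and Methodology) adds that persisting thromboembolic risk can call for indefinite apixaban. Section 5.4.1 allows a later reduction: "consideration will be given for decreasing the apixaban dose to 2.5 mg twice-daily after 6 months for the remainder of the study".

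Section 3.5 also says what happens to the subject's study participation after apixaban stops. There is no automatic withdrawal, and efficacy and safety follow-up continues. If the stop is permanent and comes before the 6-month visit, there is an unscheduled visit plus the remaining ones. Adverse events are described in a narrative and entered in the eCRF.

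**The concern.** The criterion points the wrong way. A new reason to anticoagulate would ordinarily be a reason to keep a subject on a therapeutic anticoagulant, or to change its dose or type. Here it is listed as a reason to stop the one in use, with no test of whether that drug already suits the condition and no statement of what replaces it. These subjects have had a recent intermediate-high-risk PE. An investigator who follows the text would move a subject off apixaban even where continuing it, or restoring its full dose, would be appropriate. An investigator who uses clinical sense instead would depart from a written criterion. What is at stake is clarity of care during follow-up.

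**Working it through.** No arithmetic applies. The question is whether the provisions fit together and whether another section fills the gap.

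**1. Does the criterion apply to conditions that apixaban treats?** Yes. It names VTE, and Section 4.1.1 describes apixaban as approved for treating and preventing exactly that. It has no qualifier limiting it to conditions needing a different agent or to failure of apixaban.

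**2. Is it a stop or a pause?** It sits in the discontinuation list, apart from the interruption list, which supports reading it as a lasting stop. This is an inference. The text says a subject should be discontinued. One neighbouring item, on the subject's own request, adds that the stop is permanent, and the sentence on visits is conditional on a permanent stop.

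**3. Where does the conflict bite?**

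| Situation | Rest of the protocol | Section 3.5, literally |
|---|---|---|
| Persisting VTE risk | Reason for indefinite apixaban (synopsis) | A new prophylaxis need is a reason to stop it |
| VTE on 2.5 mg twice daily | The protocol's own PE regimen is apixaban 10 mg, then 5 mg, twice daily | Reason to stop it |
| VTE on full-dose apixaban | Not addressed as treatment failure | Reason to stop it; defensible |
| New atrial fibrillation | Not addressed | Reason to stop it, whether or not apixaban would suit |

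The second row depends on the dose having been reduced. Section 5.4.1 makes that optional, and Section 4.1.1 describes 5 mg twice daily for 12 months.

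**4. Does another section name the next treatment?**

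- Section 3.5, after the interruption list, lets the investigator "decide when and if the apixaban can be restarted". That concerns resuming apixaban after a pause.
- Section 5.4.1 leaves the total duration of anticoagulation to the treating physician, but does not name a replacement drug.
- Section 5.4.1, follow-up visits, lists "Changes in anticoagulant medications" as something to record.
- Section 5.5 mentions an IVC filter for recurrent PE despite therapeutic anticoagulation, within rescue for hemodynamic collapse.
- Section 3.4.1 lists warfarin, other factor Xa inhibitors, fondaparinux, low molecular weight heparins and direct thrombin inhibitors among drugs that "may increase the risk of bleeding and will not be concurrently administered during the study". It does not say whether this ends when apixaban ends.

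None gives the replacement or its timing. By contrast, the alteplase part of Section 3.5 does give next steps: treatment at the investigator's judgment, then apixaban once the subject is stable and anticoagulation is an option.

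**5. Does it reach the primary endpoint?** No. Section 5.4.1 starts apixaban 24 hours or more after study drug and only once the post-intervention evaluations are complete. The repeat CTA is one of these, so a rule about stopping apixaban cannot act before it. The sample size in Section 7.1.1 rests on imaging outcomes at that scan and is also unaffected.

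**The case against.** The best defence is that the literal reading is not the intended one. Every subject already has a PE, so developing VTE must mean a new event on treatment, and leaving apixaban after such a failure is a reasonable choice. The synopsis lets the investigator decrease or discontinue apixaban after an adverse event, and the site has a specialist PE team.

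Part of this stands. Recurrence on full-dose apixaban can properly be treated as failure, and the revised criterion should allow for it. But the defence does not cover a new prophylaxis need, atrial fibrillation, or a VTE on the reduced dose. The discretion in the synopsis runs only towards less apixaban or none, so it does not cure the rule.

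A reader might infer more than the documents support:

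- *That all anticoagulation must stop, or that switching is forbidden.* The criterion concerns apixaban alone, and Section 3.4.1 excludes concurrent use. A sequential switch is unspecified, not prohibited.
- *That the protocol is silent on what follows.* It specifies follow-up, visits and reporting. Only the treatment is missing.
- *That the chance of harm can be estimated from the apixaban trial in Section 1.1, where 21 of 900 PE patients had the primary efficacy outcome.* The protocol does not define that outcome or give its dose or follow-up time. Scaling it to 40 subjects would at best count any VTE on apixaban, including failures where switching is right. It would not measure harm from the wording.

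**Conclusion.** The criterion is wrong as written, with low severity. It makes a new need for anticoagulation a reason to stop the trial's anticoagulant, against that drug's stated role in the same protocol, and leaves the replacement and its start unstated. This rests on the text alone and assumes only that the criterion is read as it stands. Whether every such stop is permanent is inferred from its placement, but the conflict does not depend on it.

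The consequence is an avoidable ambiguity in subject care. There is no effect on the 24-hour RMMS endpoint or the sample size. Any effect on the secondary comparison of recurrence with historic controls is likely minor and cannot be quantified from the documents. No rate is given for new atrial fibrillation or new prophylaxis needs.

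**What to change.** Replace the criterion in Section 3.5 with:

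> The subject develops a condition that, in the investigator's judgment, requires an anticoagulant other than apixaban (which may include recurrent VTE on full-dose apixaban); the replacement is started when apixaban is stopped. Otherwise apixaban is continued, with the dose adjusted if needed.

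Add to Section 3.4.1 that the listed anticoagulants are allowed after apixaban has been permanently discontinued.

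The cost is one reworded criterion and one added sentence, through the usual amendment and IRB route. No visits, data items or subjects are added, and the statistical analysis does not change.

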	After delivery of the systemic (IV) tPA/placebo, patients will continue IV unfractionated heparin therapy for at least 24 hours. If there is no evidence of active bleeding nor significant hemoglobin drop (i.e., $\geq 2 \text{ mg/dL}$), patients will be transitioned to standard dose apixaban, 10 mg twice-daily x one week followed by 5 mg twice-daily for at least 6 months. Some patients will require indefinite apixaban therapy based on patient-specific factors, including unprovoked nature of PE event, and/or persisting DVT/PE risk factors. Finally, consideration will be given for decreasing the apixaban dose to 2.5 mg twice-daily after 6 months. Apixaban was selected as the anticoagulant of choice due to its very favorable bleeding profile in large clinical trials, which is an important consideration when prescribing an anticoagulant following systemic thrombolysis.
	Within 24 \pm 8 hours post study drug infusion, a repeat chest CTA and echocardiogram will be performed. sPESI will also be calculated at this timepoint.

٦

	At Day 30, 180 and 365, all subjects will have clinic visits which will include a physical exam, repeat echocardiogram (at Day 30 & 180), 6 minute walk test (6MWT), quality of life questionnaires, assessment of adverse and bleeding events and a review of concomitant medications including compliance with apixaban. At Day 3, 7, 90 and 270, a remote health check will occur via telephone or email assessing adverse and bleeding events, alongside a review of concomitant medications (including an assessment of compliance with apixaban).
	If any subject experiences an adverse event (AE), the investigator may, at his or her discretion, decrease or discontinue the study drug or apixaban.
	The DMC will meet after 10 subjects are enrolled; bleeding and other complications will be reviewed. An interim analysis will occur after 20 subjects have completed Day 30. The DMC will meet again after 30 subjects have completed Day 30. Because it is a single-center study, the investigators and study coordinators will be acutely aware of all adverse events.
	The primary analyses will compare the clot lysis on CTA in treatment A at 24 hours post study drug infusion. See Section 7 for a complete discussion of the statistical analysis.

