2.2. INSTITUTIONAL REVIEW BOARD

Before study initiation, we will obtain a written and dated approval letter from the Cedars-Sinai Medical Center IRB for the protocol, consent form, HIPAA Authorization form and all recruitment materials. The investigator will provide the IRB approval letter, stamped approved consents and recruitment materials to the BMS/Pfizer Alliance.

The investigator will provide the BMS/Pfizer Alliance and Cedars-Sinai Medical Center IRB with Serious Adverse Events (SAEs), protocol deviations and Data Safety Monitoring Board correspondences.

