4.3. BLINDING AND UNBLINDING

All study personnel except the research pharmacy team will be blinded to intervention groups. The treatment medication and placebo will be prepared in similar IV bags and volumes. Assessments regarding clinical recovery will be conducted by an assessor blind to treatment allocation.

To maintain the overall quality and legitimacy of the clinical trial, unblinding should occur only in exceptional circumstances when knowledge of the actual treatment is absolutely essential for further management of the patient.

The Investigator is encouraged to maintain the blind as far as possible. The actual allocation must NOT be disclosed to the patient and/or other study personnel including other site personnel, monitors, BMS/Pfizer Alliance or project office staff; nor should there be any written or verbal disclosure of the code in any of the corresponding patient documents.

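### The stopping criteria, including one fatal intracranial hemorrhage, apply only at the single 20-subject interim: no listed event triggers a hold, and later events meet no stated criterion

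*Combined protocol and SAP*

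**What the plan says.** Section 3.5, under withdrawal from the study, opens the list with "Stopping rules at the interim analysis for the treatment (tPA) group would involve". Three of its criteria concern serious bleeds within 72 hours:

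- a single intracranial hemorrhage (ICH) that proves fatal;
- a second ICH, whether fatal or not;
- a limit on other serious bleeds, worded as "Severe or life-threatening bleed rate of 15%; i.e., three patients (GUSTO criteria").

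A fourth counts two in-hospital deaths from acute PE, in either group. A catch-all closes the same list: "Any other issue that the DMC believes merits discontinuing the trial".

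The Synopsis (Study Design and Methodology) defines one such analysis: "An interim analysis will occur after 20 subjects have completed Day 30". It also schedules DMC meetings at 10 and at 30 subjects, and observes that investigators at a single center will know of every adverse event. The Synopsis safety entry adds that no more than 3 further subjects may enter until the DMC has approved continuation after the first 10. Section 6.3.1 mentions only the 10-subject meeting and refers to a charter.

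On reporting, Section 2.2 says "The investigator will provide the BMS/Pfizer Alliance and Cedars-Sinai Medical Center IRB with Serious Adverse Events (SAEs), protocol deviations", and Section 8.1.1 sends SAEs to the funder within 24 hours or one business day. On blinding, Section 4.3 says "All study personnel except the research pharmacy team will be blinded to intervention groups".

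**The concern.** A threshold of one or two events is normally meant to act when the event happens. Here it is tied to a recruitment milestone. Section 3.5 stops the infusion in the affected subject, but no section pauses randomisation or calls an ad hoc DMC meeting. After the interim no listed criterion applies, because the catch-all sits under the same heading.

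The informal safeguard is weak for the bleeding criteria. They count events on tPA, and the investigators who see the events are blinded. Section 4.3 allows unblinding only where a patient's further management requires it. The documents supplied do not say that the DMC, which would apply the criteria, is told of an event between its meetings.

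At stake is continued randomisation to a thrombolytic after an event that the sponsor itself has named as a reason to stop.

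**Working it through.** **The plan's own figure.** The bleeding limit equates 15% with three patients: 3/20 = 15%. Twenty is either all interim subjects or the full tPA arm. At 1:1 about 10 tPA subjects are past Day 30 at the interim, and 3/10 = 30%. At the 10- and 30-subject reviews (about 5 and 15 on tPA) three patients would be 60% and 20%.

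**Early events.** The cap is 10 + 3 = 13 subjects until the DMC approves. An event in subject 1, 5 or 10 is followed by at most 12, 8 or 3 more. Section 5.2 counts enrolment from consent, so the number randomised may be smaller.

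**Events between the cap and the interim, and after it.** Inputs: 40 subjects (Synopsis); study up to 24 months with about 1 year per subject (Section 3.2). Accrual is then 24 − 12 = 12 months (derived; 6 to 18 shown as a range), at a steady rate.

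- Accrual in 30 days: 40 × 30/365.25 = 3.3 subjects.
- Randomised when subject 20 reaches Day 30: 20 + 3.3 = 23.3.
- After an event in subject 14, before the interim: 23.3 − 14 = about 9.
- Randomised after the interim: 40 − 23.3 = about 17.
- Randomised when subject 30 reaches Day 30: 30 + 3.3 = 33.3, so about 7 enter after the last scheduled DMC review.

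| Accrual | Randomised at interim | More after an event in subject 14 | Randomised after interim |
|---|---|---|---|
| 6 months | 26.6 | about 13 | about 13 |
| 12 months | 23.3 | about 9 | about 17 |
| 18 months | 22.2 | about 8 | about 18 |

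The flowchart allows Day 30 a window of 15 days. If the 20th visit falls at day 45, the interim comes with 24.9 randomised under 12-month accrual, leaving about 15.

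**Chance that the first fatal ICH falls in tPA patients 11 to 20.** With rate p, this is [1 − (1 − p)^20] − [1 − (1 − p)^10]. The rates are assumptions; the documents give no fatal ICH rate for this regimen.

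| p | At least one in 20 | At least one in first 10 | Difference |
|---|---|---|---|
| 0.5% | 9.5% | 4.9% | 4.6% |
| 1% | 18.2% | 9.6% | 8.6% |
| 2% | 33.2% | 18.3% | 14.9% |

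If the interim also counts tPA subjects treated but not yet at Day 30 (about 12 in all), the difference is (1 − p)^12 − (1 − p)^20 = 3.7%, 6.8% and 11.7%.

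**The three-patient limit.** If the true severe-bleed rate were 15%, the rate that the rule names, the binomial chance of three or more is 18.0% in 10 tPA subjects and 59.5% in 20. In 59.5 − 18.0 = 41.5% of such trials the count is reached only after the interim. At a true 5% the chances are 1.2% and 7.5%.

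**The case against.** The plan has more oversight than the stopping list alone suggests, and several stronger readings fail.

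- A reader might infer that an event in subject 1 would be followed by 22 to 24 randomisations before anything happens. That counts to the interim and ignores the cap, which requires DMC approval at 13 subjects; the limit is 12 more, about 6 on tPA. That hold is scheduled rather than triggered by an event, and it carries no criteria.
- A reader might infer that nothing can stop the trial earlier, or that later events go unreviewed. The DMC meets again at 30 subjects. Sections 6.1.2, 8.1.1 and 9.7 leave room for the funder, sponsor or authorities to halt or end the study. These routes stand, but they are discretionary.
- A reader might take the tenecteplase trial described in Section 1.1 (12 strokes = 2.4%, so n = 500; 10 hemorrhagic = 2.0%) and infer a 33% chance of a stopping event in 20 tPA subjects and 15% in the last 8. Those are chances of any one hemorrhagic stroke within 7 days on another drug. The criteria need a fatal ICH, or two, within 72 hours. At 2%, two or more ICH has probability 6.0% in 20 subjects and 1.0% in 8.
- Blinding does not hide every limit: the PE-death criterion covers either group.
- The charter may provide for ad hoc meetings, SAE routing and unblinded allocation. It was not supplied, so the point about routing rests on silence. A charter provision would still have to be squared with the explicit interim-only wording of Section 3.5.

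**Conclusion.** The point holds as a gap in when and how the criteria act. As written they are consulted once, no listed event triggers a hold or a DMC meeting, and no stated criterion covers the 10- and 30-subject reviews or any event after the interim. This rests on the text, not on an event rate.

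Its size is moderate. The cap bounds early events. Beyond 13 subjects there is no bound: about 9 further randomisations could follow an event in subject 14, and about 17 subjects (13 to 18 for accrual over 6 to 18 months) enter after the interim. The chance that a first fatal ICH falls in the second half of the tPA arm is 4.6% to 14.9% over assumed rates of 0.5% to 2%. The counts assume steady accrual and the probabilities assume independent patients. The conclusion is limited by the unseen charter.

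**What to change.** Keep the sponsor's own thresholds and change only when and how they operate.

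1. Reword Section 3.5 so that the event-count criteria apply from the first infusion to the last. When one may have been met, randomisation is held until the DMC has met and recommended restart.
2. Add the DMC to the recipients of ICH, GUSTO severe bleeds and deaths on the existing 24-hour timeline, with allocation passed from the unblinded research pharmacy to the DMC alone.
3. State the denominator of the 15% limit. As a rate it matches only 20 patients, so it should not be carried unchanged to reviews with about 5, 10 or 15 tPA subjects.
4. Reconcile the Synopsis (study design and safety entries), Section 3.5, Section 6.3.1 and the charter on when each review falls and which criteria apply. The first review is placed at 10 enrolled in one entry and at 10 past Day 30 in others, and the cap appears only in the Synopsis.

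The cost is protocol and charter wording, an occasional short pause in enrolment and an ad hoc DMC call. The sample size and primary analysis are unaffected.
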